**Note:**

**CAPS-5** = Clinician Administered PTSD Scale for DSM-5; **C-SSRS** = Columbia-Suicide Severity Rating Scale; **DIAMOND** = Structured Diagnostic Interview for Anxiety, Mood, OCD and related Neuropsychiatric Disorders; **Ohio TBI Screen** = Ohio Traumatic Brain Injury Screen; **PCL-5** = PTSD Checklist- Identified Patient Version; **PHQ-9** = Patient Health Questionnaire; **GAD-7** = Generalized Anxiety Disorder – 7-item; **PTCI** = Post-Traumatic Cognitions Inventory; **ADL** = Activities of Daily Living; **AUDIT-C** = Alcohol Use Disorders Identification Test; **DAST-10** = Drug Abuse Screening Test; **CD-RISC-10** = Connor-Davidson Resilience Scale – 10 items; **PROMIS-SF-8** = Patient-Reported Outcomes Measurement Information System Satisfaction with Participation in Social Roles Short Form; **PROMIS-SD-SF** = Patient-Reported Outcomes Measurement Information System Sleep Disturbance Short Form; **PROMIS-SRI-SF** = Patient-Reported Outcomes Measurement Information System

Sleep-Related Impairment Short Form; **RAND-12+** = The Veterans Rand 12-Item Health Survey; **FFQ** = VioScreen Food Frequency Questionnaire

\*Fecal collection will take place within one day of the assessment and prior to the following assessment. The CPT-5 Day 1 sample should ideally be collected on Sunday, one day before the first session, or as soon as possible after. For participants who did not complete the intensive CPT, follow-up intervals will follow the same schedule as for individuals who complete treatment.

†These assessments will not be administered to participants who opt to participate via telephone/video.

Biological sample collection will involve the collection of fecal- and oral-derived microbiota, salivary cytokines, and human DNA from whole saliva. Fecal samples will be collected by participants using a home collection kit. Participants will be provided instructions and all necessary equipment for sample collection and storage by a member of the study staff and will bring samples to their next treatment session. For participants completing telephone/video session, a home fecal sample collection kit as well as sample collection instructions, storage instructions and pre-paid return mailing information will be shipped to them. Salivary samples will be collected by study staff during study visits. Participants will be instructed to drink water prior to the session to ensure hydration and to rinse their mouth with water 10 minutes before the testing session with no other food or drink after. Participants will be instructed to refrain from the following activities prior to the saliva testing sessions: visiting the dentist within 48 hours, drinking alcohol and taking over-the-counter medications within 24 hours, drinking caffeine, smoking, and engaging in vigorous exercise within 2 hours, eating a major meal within 1 hour, and eating or drinking products with dairy, high levels of sugar, or high acidity within 20 minutes. Salivary cytokines and oral microbiota samples and human DNA from whole saliva will be collected by a member of the study staff during the study visit.

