## **Examining Changes in Microbiota over the Course of PTSD Treatment**

The overall goals of this project are to evaluate the use of 5-day intensively-delivered Cognitive Processing Therapy to treat PTSD and to determine the associations between the microbiome, salivary cytokines, and the presence of and recovery from PTSD. Specifically, this study is designed to 1) determine whether individual Cognitive Processing Therapy (CPT) delivered twice per day over 5 consecutive days (CPT-5) is tolerable, acceptable, and effective in reducing PTSD symptoms, 2) determine the microbial signatures associated with PTSD, 3) evaluate whether the abundance and composition of microbiota and salivary cytokine levels change over the course of PTSD treatment, and 4) examine whether changes in microbial signatures are associated with changes in cytokine levels.

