### **Scientific Review:**

Cognitive Processing Therapy (CPT) is an evidence-based psychotherapy for posttraumatic stress disorder (PTSD; Resick, Monson, & Chard, 2016) that has demonstrated efficacy and effectiveness in a large range of settings and a variety of populations (Monson et al., 2006; Resick et al., 2017; Resick, Nishith, Weaver, Astin, & Feuer, 2002; Resick, Williams, Suvak, Monson, & Gradus, 2012). Clinical outcome data from the Road Home Program Intensive Outpatient Program (IOP), which offers CPT daily over the course of three weeks to treat veterans with PTSD, show that participation in the IOP produces large PTSD and depression symptom reductions. This suggests that patients are able to safely and effectively work on their trauma on a daily basis with CPT and that the daily delivery of CPT may also be acceptable and effective.

While existing evidence-based interventions for PTSD, such as CPT, have been shown to be effective for the treatment of the disorder, it has also been suggested that underlying biology may contribute to treatment refractory PTSD. The microbiome has received increased attention and been proposed as an important factor that impacts brain function and mental health through what is referred to as the gut-brain-axis (Carabotti et al., 2015; Collins et al., 2014; Heijtz et al., 2011). However, it has yet to be determined what role microbiota play in PTSD and whether the abundance of various microbiota changes over the course of evidence-based PTSD treatment.

The proposed project will address these questions by examining microbial signatures of individuals with PTSD to establish whether previously identified microbial signatures (cf. Hemmings et al., 2017) can be found in another sample and whether those signatures can be found in oral microbiota in addition to fecal microbiota. The project will also examine whether microbial signatures change over the course of PTSD treatment to determine whether symptom improvement and changes in inflammatory marker levels are associated with changes in microbiota.

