### **Biosample Analysis:**

To assess whether microbial signatures change over the course of PTSD treatment and are different with regards to diversity and total abundance for trauma-exposed individuals with PTSD, total microbial DNA will be extracted from oral saliva and colonic fecal samples and processed using high-throughput 16S ribosomal RNA gene Illumina amplicon sequencing followed with bioinformatics analysis at RUMC. Human DNA will also be extracted from whole saliva and processed. De-identified samples may be transferred to a qualified external laboratory upon the completion of the study solely for the purposes of processing and analysis.

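### The saliva preparation list omits tooth-brushing, flossing and mouthwash, so varying mouth cleaning adds noise to Aim 3 and can create a spurious oral microbiota–cytokine correlation in Aim 4

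*Protocol*

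**What the plan says.** The biological sample collection paragraph of the protocol's Measures section gives timed rules for eight kinds of exposure before a saliva visit. The first six are "visiting the dentist within 48 hours, drinking alcohol and taking over-the-counter medications within 24 hours, drinking caffeine, smoking, and engaging in vigorous exercise", with 2 hours applying to the last three. The other two are "eating a major meal within 1 hour, and eating or drinking products with dairy, high levels of sugar, or high acidity within 20 minutes". Participants must also "rinse their mouth with water 10 minutes before the testing session with no other food or drink after". The sentence is complete and ends there.

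The same paragraph has all saliva specimens taken together, at a visit: "Salivary cytokines and oral microbiota samples and human DNA from whole saliva will be collected by a member of the study staff during the study". The assessment schedule places oral microbiota and salivary cytokines at the same five points: intake, CPT-5 Day 1, 1 week post, 1 month and 3 months. Under Biosample Analysis, "total microbial DNA will be extracted from oral saliva and colonic fecal samples". No cytokine source other than saliva is named.

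Aim 3 in the opening statement of goals concerns change in microbiota and salivary cytokines over treatment. Aim 4 is to "examine whether changes in microbial signatures are associated with changes in cytokine levels". The trial is single-arm. The SAP has no model for microbiota or cytokines.

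**The concern.** The protocol already treats the state of the mouth before sampling as important: it bars dental visits for 48 hours and asks for a water rinse. Yet a participant who follows every rule may brush, floss and use an antiseptic mouthwash shortly before the visit. These acts remove or kill oral bacteria, and brushing or flossing can put blood into saliva. The rinse is the same for everyone, so it does not even out what was done before it. After it, only food and drink are barred.

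One mouth supplies both measurements, so a single disturbance can move both. That matters most for Aim 4, where changes in one are related to changes in the other. An association produced this way would say nothing about "brain function and mental health through what is referred to as the gut-brain-axis", which motivates the study. With no comparison group, nothing in the design would expose it. The protocol also fixes no clock time for saliva collection, and the visits differ in kind (intake over one or two days, a therapy day, assessment visits), so time since mouth cleaning can plausibly vary.

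**Working it through.** **Is the omission real?** Oral hygiene was looked for in every place that could restrict or record it.

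- Protocol, Measures (saliva preparation): eight exposures and a water rinse; no brushing, flossing or mouthwash.
- Protocol, Exclusion Criteria: antibiotics, corticosteroids, diet changes and digestive surgery appear; oral hygiene does not.
- Protocol, assessment schedule: diet is recorded; mouth cleaning is not.
- Protocol, Biosample Analysis: extraction and sequencing only.
- SAP, Data analysis: models for symptom outcomes only, so no adjustment is specified.

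**Is there a planned figure to reproduce?** No. The SAP's one power statement (over 90% with over 15 participants) concerns PTSD and depression. What follows is illustrative and rests on assumed values.

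**Aim 4, by variance share.** Let a shared cleaning factor explain a share f of the variance of both change scores (one oral taxon, one cytokine), with no true link. The induced correlation is then r = f. By Fisher's z, the rejection rate of a two-sided 5% test is

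Φ(atanh(f)·√(n−3) − 1.96) + Φ(−atanh(f)·√(n−3) − 1.96).

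Worked case, f = 0.20 and n = 80: atanh(0.20) = 0.2027; 0.2027 × √77 = 1.779; Φ(−0.181) + Φ(−3.739) ≈ 0.428.

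| Share f | n = 80 | n = 40 | n = 20 |
|---|---|---|---|
| 2% | 5.4% | 5.2% | 5.1% |
| 5% | 7.2% | 6.1% | 5.5% |
| 10% | 14% | 9% | 7% |
| 20% | 43% | 23% | 13% |
| 30% | 78% | 47% | 25% |

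The value n = 80 is the enrolment target in Study Population. It is a ceiling, because biosamples are optional and telephone/video participants give no saliva. The values 40 and 20 are assumptions.

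**Aim 4, by size of shift.** Let recent cleaning occur with probability p₁ and p₂ at two visits, and shift both measures by d visit-level SDs. With V = p₁(1−p₁) + p₂(1−p₂), the induced correlation is r = d²V/(2 + d²V). At p₁ = p₂ = 0.5, V = 0.5:

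- d = 0.25: r = 0.015, false-positive rate about 5% at n = 80
- d = 0.5: r = 0.06, about 8%
- d = 1.0: r = 0.5/2.5 = 0.20, about 43%
- d = 1.5: r = 0.36, about 91%

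Solving for d, shares of 10%, 20% and 30% need shifts of about 0.67, 1.0 and 1.3 SD in both measures when half of participants have recently cleaned. When 80% have, they need about 0.8, 1.25 and 1.6 SD. If nobody cleans within the window, V = 0 and r = 0.

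**Aim 3.** The induced mean change is d(p₂ − p₁).

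- If p₁ = p₂ it is zero, and cleaning only adds d²V to the variance of the change.
- If cleaning rises from 30% to 60% (V = 0.21 + 0.24 = 0.45), the mean change is 0.15 SD at d = 0.5 or 0.30 SD at d = 1.0. At n = 80 the rejection rate is then about 15% or 40%.

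**The case against.** The strongest reply is that the protocol is already careful about the mouth. Dental visits, smoking, and dairy, sugary or acidic products are restricted and a rinse is required, so what is missing is one class of oral exposure from a detailed list. That is right, and the point claims no more.

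A reader might infer from the upper rows of the table that Aim 4 is likely to give a false result. The documents do not support that. They give no effect of mouth cleaning on any taxon or cytokine. Shares of 20% to 30% need shifts of at least about 1 SD in both measures, and at 2% to 5% the error rate is close to nominal. A shared mouth factor of that size could also include salivary flow or gum state, which a brushing rule would not remove. The saliva n is not stated and is probably below 80: the SAP describes virtual treatment and a small sample. Nor do the documents specify a 5% test for Aim 4.

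A reader might also infer that Aim 3 would show a false change over treatment. That needs mouth cleaning, or visit timing, to shift systematically between time points, and nothing in the documents says that it does. There are two pre-treatment saliva collections (intake and CPT-5 Day 1), which allow some check on fluctuation unrelated to treatment. Fecal microbiota, collected at the same five points, are not exposed to the problem.

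Finally, one might want the fecal–cytokine association made the main Aim 4 analysis. The Scientific Review makes oral microbiota an explicit purpose alongside fecal microbiota, and a fecal analysis would still carry the noise in the cytokines. Re-ranking is a debatable trade-off that this gap does not require.

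A separate participant instruction sheet might contain a brushing rule, but neither document refers to one. The omission and the shared-specimen path both stand.

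**Conclusion.** The gap is real and cheap to close. It affects only in-person participants who give saliva. Uncontrolled mouth cleaning adds noise to the saliva measures in Aim 3 and can induce a correlation between oral microbiota change and cytokine change in Aim 4. The Aim 4 effect needs only visit-to-visit variation that moves both measures; a false mean change in Aim 3 needs a systematic shift as well.

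The size is unknown. It runs from negligible, if cleaning explains a few per cent of the variance of both change scores, to serious, if it explains 20% or more and the saliva sample is near its ceiling. The case for acting rests on the low cost and on the protocol's own attention to the state of the mouth, not on the upper end of that range.

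**What to change.** 1. Add brushing, flossing and mouthwash to the existing pre-saliva restrictions for all five collections, for example in the 2-hour line with caffeine and smoking. The documents do not determine the window, so the study team should choose it.
2. Record time since last mouth cleaning at each saliva visit, so that compliance can be checked and the variable used in a sensitivity analysis.
3. Report the fecal microbiota–cytokine and oral microbiota–cytokine associations separately, and note that the oral one may be local to the mouth. Leave the ranking within Aim 4 as it is.

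The cost is one more participant instruction, one recorded item and one sentence in the analysis plan. For saliva already collected, only the third step can still be applied in full.

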### **Biosample Analysis:**

To assess whether microbial signatures change over the course of PTSD treatment and are different with regards to diversity and total abundance for trauma-exposed individuals with PTSD, total microbial DNA will be extracted from oral saliva and colonic fecal samples and processed using high-throughput 16S ribosomal RNA gene Illumina amplicon sequencing followed with bioinformatics analysis at RUMC. Human DNA will also be extracted from whole saliva and processed. De-identified samples may be transferred to a qualified external laboratory upon the completion of the study solely for the purposes of processing and analysis.

### **Risks:**

The risks associated with this study are no greater than those associated with standard evidence-based treatment for PTSD. This study uses CPT, an existing evidence-based treatment for PTSD that has been shown to be both effective and safe. To date, no adverse events have been associated with intensive CPT, suggesting that intensively-delivered treatment is tolerable.

It is possible that participants may experience distress during CPT treatment. Participants' suicidality will be assessed by the treating clinicians on an ongoing basis and assessed formally

at the intake, 1-week post-treatment, 1-month follow-up, and 3-months follow-up assessment points using the Columbia Suicide Severity Rating Scale (C-SSRS). If a participant indicates having “Thoughts that [they] would be better off dead or of hurting [themselves] in some way” more than half the days (2) or nearly every day (3), the study clinician will conduct a safety assessment. If any participant becomes actively suicidal with intent, the study clinician will refer the participant to a higher level of care (i.e., psychiatric, medical, or emergency services). All sessions will take place during regular business hours, and clinical staff will be present and available to assist in the case of a crisis during an in-person session. In the case of a crisis during a telephone/video session, the study clinician will be available to assist or will instruct the participant to call 911 or go to their nearest emergency room. Prior to the start of any telephone/video session, the provider will inquire about the current location to have this information in case of an emergency. Individuals will no longer be able to continue this course of CPT if they are actively suicidal, but may be able to enroll at a later time after reaching stability per eligibility requirements.

While risk is minimal, a loss of confidentiality is possible, although unlikely. All study staff will work diligently to ensure that all data is stored securely and that study-related files are password protected so that only members of the study staff will have access to identifiable data. To protect confidentiality, each subject is assigned a unique code. Only study personnel will be able to link patient name to the identification number. All telephone/video sessions will be conducted using HIPAA compliant platforms. In addition, a Certificate of Confidentiality will be obtained. No identifiable data will ever be disclosed to any outside parties. De-identified data may be reported in aggregate for internal clinical use, publications, or other presentations.

### **Benefits:**

Participants in this study may experience direct benefits. Given that CPT is an effective evidence- based treatment for PTSD, it is likely that participants may experience a significant reduction in their PTSD and depression symptoms by the end of treatment. The reduction in symptoms may enable participants to re-engage in daily functions. Participants may help advance our understanding of PTSD treatment and its biological effects on the body. Findings from this study may allow researchers to learn more about the physiological biomarkers associated with PTSD and how they are impacted by the current clinical practices that are used to treat individuals with PTSD.

### **Data Storage:**

#### **Specify the site at which the data will be stored and how it will be stored:**

Audio recordings, video recordings, copies/scans of CPT session materials, and all electronic data collected through computerized tasks, the internet-based assessment, and Qualtrics-delivered self-report assessments will be de-identified, password-protected, and stored in a restricted folder within the RUMC secure network infrastructure. Audio recordings will be uploaded to the secure server within one business day and will be deleted from the recording device immediately upon upload. Telephone/video visit audio and video recordings from the HIPAA compliant telephone/video platform will be uploaded to the secure server within one

business day and will be deleted from the platform immediately upon upload. CPT worksheets electronically uploaded to the secure folder accessible only to the participant and study staff will be deleted from this folder following the participant's final study visit. Copies of the worksheets will be saved to a separate restricted study folder on the RUMC network infrastructure. When personally identifying data cannot be removed (as may be the case with audio or video files), they will be provided with a unique de-identified code and stored in a separate and secure network location.

Saliva and fecal samples will be stored in a -80 degree freezer in the locked laboratory of the Department of Psychiatry and Behavioral Sciences at RUMC until analyzed. No biological data sources will contain information that will personally identify subjects. To protect confidentiality, each subject is assigned a unique code for these specimens. Only study personnel will be able to link patient name to the identification number. All information and data related to the biological specimens collected in the study will be kept in a password protected computer file on the Department of Psychiatry and Behavioral Sciences secure server or in a secure locked cabinet in the Department of Psychiatry and Behavioral Sciences.

#### **How long will the data be maintained and/or stored?**

All biological and electronic data collected will be stored for least 5 years. Once the necessary analyses have been conducted after at least 5 years, all data will be securely deleted from the secure, password-protected file and system. Saliva and fecal specimens will be destroyed once necessary analyses have been conducted.

#### **Who, other than the specified study team, will have access to the study records or data? Specify their name, role, and affiliation.**

The principal investigator will monitor all access to data. Only study staff listed on and approved by the IRB will have access to the data for research purposes. Audio and/or video recordings may be shared with approved external collaborators for analysis through encrypted software shared on a secure web-based storage site. Participants in audio and/or video recordings will be identified by coded subject IDs. Upon completion of data collection, de-identified samples may be transferred to a qualified external laboratory solely for the purposes of conducting laboratory assays to generate necessary data for the study team. This laboratory will not utilize data generated from specimens for research purposes.

In line with the NIH Guidance on Consent for Future Research Use and Broad Sharing of Human Genomic and Phenotypic Data Subject to the NIH Genomic Data Sharing Policy ([https://osp.od.nih.gov/wpcontent/uploads/NIH\\_guidance\\_elements\\_consent\\_under\\_gds\\_policy.pdf](https://osp.od.nih.gov/wpcontent/uploads/NIH_guidance_elements_consent_under_gds_policy.pdf)), some de-identified study data, including data generated from biospecimens may be placed into one or more scientific databases or shared with other researchers. Only approved researchers will be given access to these databases.

#### **Justify your needs to collect PHI in this study:**

PHI will be collected in order to characterize the participant sample and to maintain contact with participants throughout the study, deliver assessments, and document the treatment progress. The

internet-based measure (FFQ) requires the collection of PHI to identify respondents. The FFQ is an online measure delivered by VioScreen. All PHI collected from this measure will be converted to coded subject IDs before storage in the secure RUMC network infrastructure, and no PHI collected from this measure will be used for research purposes. Audio and video recordings may also contain PHI that can potentially identify respondents. As PHI cannot be removed from audio and video files, these files will be provided with de-identified codes and stored in a separate and secure network location.

